Brachycephaly is one form of DP. Brachycephaly is reported to result from the infant's head resting on a firm mattress or other solid surface when in the supine position. Common in term infants, this deformation is characterized by occipital flattening (unilateral or bilateral), ear misalignment, frontal bossing, and facial asymmetry.¹⁹ This form of DP has become more prevalent since initiation of the Back to Sleep campaign by the American Academy of Pediatrics (AAP) and other guiding agencies during the 1990's.^{5, 6, 19, 20} The Back to Sleep campaign recommends parents place their infants supine to sleep and this change in sleep position has resulted in a dramatic decline in Sudden Infant Death Syndrome.¹

Plagiocephaly is another common form of DP associated with the supine sleeping position and the Back to Sleep campaign.^{20, 21} Plagiocephaly usually results from the head being positioned in the same direction repeatedly and may or may not be related to congenital muscular torticollis.^{5, 22} With this type of head shape deformity there is asymmetry of the head shape (one side of the occiput is flattened), and ear misalignment can be present.

Dolichocephaly is a narrow, elongated head shape. This deformation develops when the infant is frequently placed in the prone or sidelying-position and is commonly seen in the premature infant population and rarely observed in full term infants.^{18, 23} The actual incidence of dolichocephaly is not known, though infants that are sick or recuperating from illness, and spend more time in their beds in the prone position, are more vulnerable to developing this type of positional head shape deformity.²³

Social Impact of Deformational Plagiocephaly

The literature is replete with documents to support the claim that the undesirable head shape and facial features associated with DP can lead to problems with parent infant attachment and social isolation as the child grows.⁸⁻¹¹ This is because parents of infants with positional head shape deformities find their infant to be less attractive. In fact, parents are so concerned about DP that a recent search of the Internet revealed a number support groups for parents, allowing them to share their concerns and obtain information about this common problem.²⁴⁻²⁷

Neurodevelopmental Impact of Deformational Plagiocephaly

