Cranial Index and Cranial Symmetry Measures: To ascertain that correction of the infant's head is achieved routine cranial index and cranial symmetry measures obtained at the NOPCO brace center, will be reviewed by the study team. The cranial index, is an objective measure that quantifies head shape by dividing the head width (M-L) by length (A-P) then multiplying it by 100% ¹⁸. The normal cranial index measurement is between 73%-85% is used to assess for brachycephaly or scaphocephaly. To assess for DP, the right anterior-posterior measures and left anterior-posterior measures will be used. For this measure, an 8mm difference in the right and left anterior-posterior measures will be indicative of asymmetry. In addition, and also as part of their routine care, a licensed orthotist will use a surface laser scanner to secure a computer image of the infant's head. The FastSCAN Handheld Laser Scanner to quickly and conveniently digitize the three-dimensional surface of the infants' head. Scanning involves smoothly sweeping the FastSCAN Wand over the infant in a manner similar to spray painting. An image of the object appears simultaneously on the computer screen. This type of measure, though fairly new, provides great detail, is reported to be nearly 100% accurate when used to make custom helmets and allows for a second set of measurements to be recorded. Measurements including A-P (length), M-L (width), Right anterior-posterior, Left anterior-posterior, and head circumference will be obtained and recorded.

Outcome Measures

Brain Magnetic Resonance Imaging (MRI): Is a routine diagnostic exam that uses a large magnet, radio waves and a computer to produce 2- and 3-dimensional images of the child's brain. This exam is FDA and does not use ionizing radiation (as in x-rays) and thus, is a way to better evaluate various parts of the body. Furthermore this type of exam is painless, since the scanner takes pictures without touching the child's body.

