In this study MRI structural data will be obtained *without sedation* prior to and following correction of DP in infants <1 year of age using an age-appropriate neuroimaging protocol that has been previously tested and used at BCH (www.babymri.org). This protocol includes intensive familiarization with MRI prior to the actual neuroimaging session, and the collection of whole brain images via MRI. A trained staff member will be on-call for all scan sessions to make this experience as comfortable as possible for infant participants and their families. ⁵⁷

The procedure for the brain MRI includes scanning each subject on a 3T Siemens Trio scanner at Boston Children's Hospital's satellite at Waltham at times best matching nap times. Imaging sessions will begin with a 1-hour conditioning session in the Mock scanner. Infants will then be rocked to sleep in the scan room and placed on the table when they fall asleep using the preparation protocol outlined in www.babymri.org where we now have a success rate of ~ 75%.⁵⁸ Once asleep in the MR scanner, imaging will be

completed in less than 45 minutes for each subject, and will include the following sequences:

3D motion corrected multiecho MPRAGE and 3D T2 SPACE. These images sequences will be used to perform semi-automatic assessment of regional and global brain volumes using FreeView.

Diffusion Tensor Imaging (DTI). DTI (an advanced MRI technique based on detecting properties of free water diffusion) can help evaluate regional and global maturation of white matter. Tractography, a newer DTI method, allows for quantification of entire white matter tracts [using measures such as anisotropy (FA) and mean diffusivity (MD)].⁵⁹ Diffusion Toolkit will be used to create the FA and MD maps and Trackvis will be used to create the tractography images.

Pseudocontinuous arterial spin labeling (PCASL). PCASL allows for quantitative estimation of both regional and global cerebral perfusion.

MRI:

Cranial index measures will be performed on 3D volumetric reconstructions of the scalp and brain using both 3D images to determine which shows more potential in quantitating interval changes. In addition both 3D T1 and T2 images will be co-registered in FreeView for semi-automatic hemispheric volumetric analysis by a trained research assistant. Lobar parcellation will also be performed.

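### The right-left difference that the protocol uses to assess DP is never taken on the MRI; only the cranial index is, and it tracks asymmetry unreliably

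*Combined protocol and SAP*

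**What the plan says.** All references are to the combined protocol and SAP.

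- **Head Shape Measures** defines two measures with different jobs. The cranial index is obtained by "dividing the head width (M-L) by length (A-P) then multiplying it by 100". Its role is stated as follows: "The normal cranial index measurement is between 73%-85% is used to assess for brachycephaly or scaphocephaly". For the condition under study the protocol turns to the other measure: "To assess for DP, the right anterior-posterior measures and left anterior-posterior measures will be used", and "an 8mm difference in the right and left anterior-posterior measures will be indicative of asymmetry".
- The same section says where both come from: "routine cranial index and cranial symmetry measures obtained at the NOPCO brace center, will be reviewed by the study team". A laser scan of the head gives a second set. Both are measures of the outer head.
- **Outcome Measures**, in the MRI paragraphs, names one linear shape measure: "Cranial index measures will be performed on 3D volumetric reconstructions of the scalp and brain using both 3D images". Its purpose is "to determine which shows more potential in quantitating interval changes".
- The other structural MRI outputs are regional and global volumes, hemispheric volumes and a lobar parcellation. No left-right contrast is defined for any of them.
- The background section on full-term infants counts brachycephaly as one form of DP. It describes plagiocephaly as another common form, in which "there is asymmetry of the head shape (one side of the occiput is flattened".

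**The concern.** The Purpose Statement wants early evidence that the shape of the vault affects the developing brain, and Aim 1 looks at brain volume and structure before and after the helmet. To relate vault to brain, the same dimension should be available on both. For asymmetry it is not. The right-left difference is recorded on the outside of the head, while the index carried onto the MRI is the one the protocol assigns to a different kind of deformity. A head and its mirror image have the same cranial index.

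What is at stake is interpretation in a sample of about 10 infants. If an infant's outer asymmetry resolves and the MRI index hardly moves, the reader cannot tell whether the brain kept its shape or whether the index did not register the change.

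**Working it through.** The protocol gives no numerical claim to reproduce here. The check asks how far the index, as the protocol defines it, moves when a known asymmetry is fully corrected.

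**Inputs from the protocol:** index = 100 x width / length; normal range 73%-85%; 8 mm marks asymmetry.

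**Assumed inputs:** an elliptical outline 120 mm wide and 145 mm long (half-axes 60 and 72.5 mm), and right and left measures taken as diagonals through the centre at 30 degrees to the midline. The protocol gives neither head size nor angle. The asymmetry is set to 12 mm.

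**Symmetric head.** 100 x 120 / 145 = 82.76%.

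**Skew with one side pushed forward** (y becomes y + kx). A diagonal has length 2 / √[(0.5/60)² + ((0.866 ∓ 0.5k)/72.5)²]. With k = 0.1125 the two diagonals are 143.52 and 131.52 mm, a 12 mm difference.
- Maximal length = 2√(72.5² + 60² x 0.1125²) = 145.63 mm; index = 120 / 145.63 = 82.40%.
- Midline length stays 145 mm; index = 82.76%.
- Full correction therefore moves the index by +0.36 points or by 0.

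**Skew with the front shifted sideways against the back** (x becomes x + ky). A 12 mm difference needs k = 0.0774.
- Width = 2√(60² + 72.5² x 0.0774²) = 120.52 mm.
- With maximal length 145 mm, index = 83.12%.
- With midline length 2 x 60 x 72.5 / 60.26 = 144.37 mm, index = 83.48%.
- Full correction moves the index by -0.36 or -0.72 points.

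Across the two skews the change is 0 to about 0.7 points, and its sign depends on the geometry. The right and left half-areas are equal before and after, because a skewed ellipse is symmetric about its centre.

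**One-sided occipital flattening**, the pattern the background section describes. The radius is reduced by a factor 1 - h·exp(-d²/2s²), where d is the angle from the right posterior diagonal, s is the breadth of the flat area, and h is solved for a 12 mm difference.

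| Breadth s | Index, maximal length | Index, midline length | Half-areas differ by |
|---|---|---|---|
| 15° | 83.5% | 83.8% | 7.0% |
| 20° | 84.5% | 85.1% | 8.4% |
| 30° | 86.3% | 87.2% | 10.9% |

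Against 82.76%, the index moves by 0.7 points at the least (83.46 - 82.76) and 4.4 at the most (87.21 - 82.76), so roughly 0.7 to 4. It can leave the 73%-85% range. The half-areas differ by about 7% to 11%, so a hemispheric volume could respond as well.

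**The measure that was left out.** In every case above, the right-left difference goes from 12 mm to 0, across the protocol's 8 mm mark.

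**The case against.** Several points on the other side stand.

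- *The index is not blind to one-sided flattening.* Correct. A reader who looked only at the skewed head might infer that the index cannot see plagiocephaly at all, or that hemispheric volumes never respond. The flattening results do not support that.
- *It is not a designated endpoint.* A reader might infer that the cranial index is the study's single brain-shape endpoint, and that no change in it would be reported as an unchanged brain. The protocol says neither. The sentence compares the two 3D image types, and no rule for reading a null result is given.
- *Other outputs may show asymmetry.* Regional, hemispheric and lobar volumes are planned. Under Data Management a neuroradiologist examines each infant for pre-post change, and Data Analysis promises a case presentation per infant. These could describe a lopsided brain becoming even. They are volumes or individual readings, however, without a defined left-right measure that matches the one on the outer head.
- *Brachycephaly is DP too.* The protocol says so, and for those infants the index is the suitable measure. The gap concerns infants with asymmetry.
- *The images are kept.* The measurement could be made later, so the omission can be repaired. That lowers the urgency. It does not supply landmarks fixed before the images are read.

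Nor do the documents support reading this as a failure to confirm correction of the head: outer symmetry is measured at the brace center.

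**Conclusion.** The point holds as a gap in measurement. The protocol's own measure for assessing DP is not specified on the scalp or brain reconstructions, and the index used there follows asymmetry inconsistently. For a 12 mm asymmetry fully corrected, it changes by 0 to about 0.7 points in a skewed head and by roughly 0.7 to 4 points with one-sided flattening.

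These sizes rest on an assumed two-dimensional outline, assumed 30-degree diagonals and assumed deformity shapes. They describe an outer contour, and a brain surface may differ. Two conclusions do not rest on the model: the index has no left-right term, and the plan names no left-right shape measure on the MRI. As a result, vault asymmetry and brain asymmetry cannot be compared directly. This is a worthwhile and inexpensive improvement to a descriptive pilot, and it does not undermine the study.

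**What to change.** In the MRI paragraphs of Outcome Measures, keep the cranial index and add the following. On the same pre and post 3D scalp and brain reconstructions, for all infants, measure the right and left anterior-posterior lengths and their difference in mm. Fix the landmarks or the angle before the images are read, and report the pre-post change beside that of the cranial index.

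The cost is a few extra linear measurements per existing reconstruction and the work of writing a landmark definition, which the protocol does not yet have for a brain surface. No new scan, sequence or visit is needed, and treatment is untouched. There is no need to assign different endpoints to different deformity types. In a sample of 10 that would split the data and raise the question of infants with both features.

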Families who attend/complete both sets of MRI measures (pre and post), will be offered a \$50 gift card at the end of the study to offset some of the gas costs incurred driving to the MRI appointments. In instances where families attempt the MRI but the baby cannot be effectively scanned due to movement, the families will still receive their gift card. Families who do not wish to attend the MRI, cancel their MRI appointments without rescheduling, or fail to arrive at their MRI appointments will not be eligible for the gift cards. The gift card may be given to the family at the end of their last MRI appointment if available, or will be mailed to them after they complete the study. If mailed to the family, they will receive a written thank you letter along with the gift card.

Comparison sample: To identify infants with similar characteristics but less severe or no DP, our neuroradiology team members will conduct a retrospective chart review from within BCH medical records. Infants with similar characteristics but with no or less severe DP as measured according to *Cranial Index and Cranial Symmetry Measures* (see *Head Shape Measures section below*) will be identified as our comparison sample. This will enable us to provide descriptive comparisons of Brain MRI axonal pathway myelination between infants with less severe or no DP.

Study Timeline

This pilot study will take approximately 1.5 years to complete.

Table 2.

Month 1	Month 2-4	Month 2-10	Month 8-10	Month 11+
IRB Application, Approval, Education of	Enrollment, Head Shape Measures	Treatment for DP	Head Shape Measures Brain MRI	Data Analysis &

clinical and study staff	Brain MRI FDNIRS/DCS MSEL		FDNIRS/DCS MSEL	Manuscript Preparation
--------------------------	---------------------------------	--	--------------------	------------------------

- Average time for treatment of DP is 4-6 months.

Head Shape Measures

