MD and FA maps will be co-registered to the volumetric data sets with mean values for the regions segmented on the co-registered volumetric data determined. Bilateral projection fiber systems (i.e. axonal pathways) passing through the internal capsule, optic radiations and the arcuate fasciculus will be segmented using standard techniques with MD and FA for each tract determined.

PCASL data sets will be co-registered to the volumetric data sets and mean perfusion values for regions segmented determined.

Frequency Domain Near Infrared and Diffuse Correlation Spectroscopy (FDNIRS/DCS): FDNIRS/DCS is a non-invasive test that involves holding an optical probe over 7 different locations on the infant's head for 10-15 seconds in each location. Data acquisition with each instrument requires repositioning of the probe due to hair and superficial large vessels to ensure that the measurement is representative of the underlying brain region. Measurement of FDNIRS/DCS may take up to 1 hour.

MRI and FDNIRS Measures: These measures will be quantified according to their respective units of measure and the investigators will prepare a report of the pre and post exam (by FDNIRS/DCS, MRI) findings, and comparing the two.

The Mullen Scales of Early Learning (MSEL):

The Mullen (Scales of Early Learning) provides a profile of cognitive ability in five areas: Gross Motor, Fine Motor, Expressive Language, Receptive Language, and Visual Reception.

This test assesses visual and language abilities at both receptive and expressive levels and provides an integrated framework within which infant development and interactional patterns can be determined. One of the theoretical features underlying the development of the MSEL is the linking of motor equilibration to early visual and language development. Central motor control and mobility have a primary role in the development of skills and abilities in the four cognitive domains of the Mullen Scales: visual reception, fine motor skills, and receptive and expressive language.

The Gross Motor Scale measures central motor control and mobility. The early Gross Motor tasks assess such skills as sitting, creeping, pulling to stand, and walking.

The Visual Reception Scale tests a child's performance in processing visual patterns. The primary ability areas are visual discrimination and visual memory. The tasks present visual information in various forms and patterns, and assess visual processing skills.

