with the MDI (.30). Similarly, the Mullen Receptive Language scale had a higher correlation with the Preschool Language Assessment Auditory Comprehension (.85) than with Verbal Ability (.72), while the converse was true with the Mullen Expressive Language Scale (.72 for auditory and .80 for verbal). Finally, the Mullen Fine Motor scale was strongly correlated with the Peabody Fine Motor Scale, across four age groups of children between the ages of 6 and 36 months (correlations ranged from .65 to .82). (2) Predictive validity: no information available.⁶⁴

Brain MRI axonal pathway

The identification of the comparison sample will enable us to provide descriptive comparisons of brain MRI axonal pathway myelination between with infants in our primary study sample against those with less severe or no DP.

Using the Cranial Index and Cranial Symmetry Measures, a comparison sample of infants (gender, age and race/ethnicity) with less severe or no DP will be identified by our neuroradiology team members through retrospective chart review from within BCH medical records. Data collection will be limited to Brain MRI and infant characteristics' data that already exists in the medical records. Data including brain MRIs and infant characteristics will be de-identified for storage. Members of the study team will maintain an electronic record of corresponding MRNs in the study log in the event that data verification or additional analyses are needed.

Axonal pathways for infants with DP primary study sample undergoing helmet therapy and those of the comparison sample will be constructed then examined for differences axonal pathways.

Data Management

Data will be managed and stored by the Cardiology Clinical & Research Regulatory Group at BCH. Baseline cranial index and cranial symmetry measurements (obtained manually and by laser scan) for each of the study subjects will be examined by one the investigators (Neurosurgeon or Plastic Surgeon) to confirm correction. Then one of the other investigators (a neuroradiologist with experience in performing FDNIRS/DCS and Brain MRIs) will examine each of the study subjects independently for changes in brain volume/structure, myelination of axonal pathways, perfusion of cerebral structures and cerebral oxygen consumption for changes pre and post correction. FDNIRS/DCS, brain MRI and MSEL data will be stored into a password protected, secure computer.

Data Analysis

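### No masking of readers or segmenters to time point or group is specified, and the MRI reader is asked directly to look for pre/post change

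*Combined protocol and SAP*

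**What the plan says.** - **Reading.** Data Management has a surgeon-investigator confirm correction first. The next step begins "Then one of the other investigators (a neuroradiologist with experience in performing FDNIRS/DCS and Brain MRIs"). This person "will examine each of the study subjects independently for changes in brain volume/structure", and the list of things to examine ends with "perfusion of cerebral structures and cerebral oxygen consumption for changes pre and post correction". Under MRI and FDNIRS Measures, "the investigators will prepare a report of the pre and post exam (by FDNIRS/DCS, MRI) findings, and comparing the two".
- **Volumetry.** The MRI part of Outcome Measures has the T1 and T2 images co-registered for "semi-automatic hemispheric volumetric analysis by a trained research assistant". What the assistant is told about the visit is not stated.
- **Regional values.** FA, MD and perfusion maps are co-registered to the volumetric data, and means are taken over the regions segmented there.
- **Tracts.** The named pathways "will be segmented using standard techniques with MD and FA for each tract determined". Software makes the FA and MD maps and the tractography images. No operator is named for the segmentation.
- **Comparison infants (Aim 3).** The Comparison sample paragraph says "our neuroradiology team members will conduct a retrospective chart review from within BCH medical records", using head-shape measures to judge severity. The section on the axonal pathway says that pathways are then built and examined for differences, without saying by whom.
- **De-identification.** It is stated for storing the comparison data, and the study team keeps a log linking back to record numbers. It is not described as masking for reading.
- **Analysis.** Data Analysis plans case presentations, descriptive statistics and, if the data allow, a signed-rank test on the paired observations.

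**The concern.** Aims 1, 2 and 4 rest on MRI values that pass through a segmentation with operator input, and Aim 3 rests on tract values with an unstated amount of it. The one reader who is described must know which scan came first, because finding change between them is the task. The Purpose Statement says what the study hopes to see: brain changes that occur with helmet therapy.

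The pre/post aims have no control group, the target is 10 infants, and no second or repeat MRI read is planned. If an operator tends to place boundaries slightly differently on post-treatment scans, nothing in the design would reveal it, and it would be reported as change. In Aim 3, the same kind of tendency between groups could appear as an effect of DP. These results are meant to inform whether a larger investigation is needed.

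**Working it through.** **Step 1: what each person is stated to know.**

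| Task | Who | Time point | Group |
|---|---|---|---|
| Pre/post reading | one neuroradiologist | known; it is the task | not applicable |
| Volumetry | research assistant | not stated | not stated |
| Tract segmentation | not named | not stated | not stated |
| Choice of comparators | neuroradiology team members | not applicable | known; it is the task |
| Case/comparator examination | not named | not applicable | not stated |

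No row contains masking. The word independently in "will examine each of the study subjects independently for changes in brain volume/structure" may mean one infant at a time, or separately from the surgeon. Neither meaning hides the visit.

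**Step 2: how far operator input reaches.** Only the volumetry is called semi-automatic. The regional means of perfusion and of the two diffusion measures use its regions, so one operator-dependent step feeds Aims 1, 2 and 4. Tract-level diffusion values depend on a separate segmentation whose manual share is unknown.

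**Step 3: sensitivity of the planned test.** The plan gives no figure for reader error, and no alpha, power, effect size or SD, so its target of 10 cannot be re-derived. Only the recruitment ceiling can be checked: 10 + 5 = 15. Everything below is therefore illustration.

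Assumptions: two-sided alpha 0.05; true change zero; normal paired differences; a constant operator shift b, in SDs of the paired difference.

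- Model: D_i = b + e_i, with e_i ~ N(0, 1).
- Statistic: W+ is the sum of the ranks of |D_i| over positive D_i. The total is n(n+1)/2 = 10 × 11/2 = 55.
- Exact cut-off at n = 10: reject when min(W+, 55 − W+) ≤ 8. Of 2^10 = 1024 sign patterns, 25 give a rank sum of 8 or less, so the attained level is 2 × 25/1024 = 0.049.
- Rejection rates for b > 0 come from 200,000 simulated samples per case.

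| Pairs | Cut-off | Attained level, b = 0 | b = 0.25 | b = 0.5 | b = 0.75 |
|---|---|---|---|---|---|
| 8 | 3 | 0.039 | 0.08 | 0.19 | 0.39 |
| 10 | 8 | 0.049 | 0.11 | 0.28 | 0.54 |
| 15 | 25 | 0.048 | 0.14 | 0.42 | 0.75 |

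The rates rise with the number of pairs. A constant shift does not average out, so recruiting to the upper limit would not help.

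**Step 4: is masked processing feasible?** The Study Timeline puts the post-treatment scans in Months 8–10 and data analysis from Month 11. Both visits' scans can therefore be in hand before segmentation starts, which is what random ordering across visits needs.

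**The case against.** **Masking would leak, and growth is the larger problem.** Treatment averages 4–6 months, during rapid brain growth, and head shape is the very thing being corrected. Cranial index is to be measured on the same 3D images, so whoever does that sees head shape. Comparison scans come from existing records and may look different. Pre/post change is confounded with growth whoever reads the scans. All of this stands, and it limits the gain. It does not remove it: single-scan processing prevents adjustment side by side, and locking prevents later revision. Confounding by growth is no reason to keep a second, avoidable source of error.

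**It is only a descriptive pilot.** This also stands, and testing is conditional on the data. The main effect is on how the descriptive changes can be interpreted.

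**Stronger readings that the documents do not support.**
- A reader might infer that the segmenting staff know visit and group. The text is silent on this. Knowledge of time point is clear only for the neuroradiologist's pre/post reading.
- A reader might infer that the tracts are drawn by hand. The plan says only that they "will be segmented using standard techniques with MD and FA for each tract determined".
- A reader might infer drift towards a helmet benefit. The aims ask neutrally whether differences exist and give no sign for volume, FA, MD or perfusion. Aim 3 concerns DP severity, so the helmet does not enter that contrast.

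**Conclusion.** The point holds as a gap in the measurement procedure, and it is worth closing because doing so is cheap. Masking is not specified at any step, the pre/post read is open by design, and at least the volumetry and the regional means that inherit its segmentation depend on an operator. With about 10 uncontrolled pairs and no repeat read, an operator tendency could not be told apart from real change.

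The size of any such tendency is unknown. The rise from 0.049 to about 0.11, 0.28 or 0.54 at 10 pairs rests on assumed shifts of 0.25, 0.5 and 0.75 SD that act equally in every infant, with normal differences and two-sided alpha 0.05. It shows how sensitive the test would be. It does not estimate bias in this study, and it should not be read as evidence that bias occurred.

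**What to change.** Amend the MRI part of Outcome Measures, the axonal pathway section and Data Management as follows.

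1. Before segmentation, strip dates, identifiers, visit and group labels, and give each scan a random code.
2. Segment scans singly, in random order across visits and groups.
3. Lock the volume, FA, MD and perfusion values before the code is broken.
4. Do the neuroradiologist's pre/post comparison and write the case reports only after the lock.
5. For Aim 3, fix the comparison list from chart and head-shape data before any tract is reconstructed.
6. State that masking is partial, because age, head shape or scan source may show, and that it does not remove the confounding of pre/post change with growth.

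The cost is a coding list and a processing order; no extra scan, reader or visit is needed. The downside is that case presentations wait for the lock. Re-reading a subset of coded scans would measure operator agreement, but it is optional because it adds reading time.
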